12.1.5 Outcome Categories for an AE

Reportable outcomes and/or sequelae of an AE may include the following:

- Recovered/resolved;
- Recovering/resolving;
- Not recovered/not resolved;
- Recovered/resolved with sequelae;
- Fatal; or
- Unknown.

If there is more than one AE, only the AE leading to death will be attributed with a "fatal" outcome.

12.2 Definition of a Serious Adverse Event (SAE)

An SAE is an adverse event that:

- led to death;
- led to serious deterioration in the health of the subject, that either resulted in:
 - o a life-threatening illness or injury;
 - o a permanent impairment of a body structure or a body function, including chronic diseases;
 - o inpatient or prolonged hospitalization; or
 - o medical or surgical intervention to prevent life-threatening illness or injury or permanent impairment to a body structure or a body function.
- led to fetal distress, fetal death, or a congenital abnormality or birth defect, including physical or mental impairment.

Note: Planned hospitalization for a pre-existing condition, or a procedure required by the CSP, without serious deterioration in health, is not considered an SAE.

12.2.1 Details of an SAE

In cases of fatality, the cause of death is considered the AE, and the death is considered its outcome. In this case, the primary cause of death (i.e., the event leading to death) should be recorded and reported as an SAE. "Death" will be recorded as the outcome of this respective event; death will not be recorded as a separate event. Only if no cause of death can be reported (e.g., sudden death, unexplained death), the death per se might be reported as an SAE. In cases of death, an autopsy report should be submitted (if available). The date and cause of death should be recorded.

Planned hospitalization for a pre-existing condition is not considered an SAE. If a subject experiences an additional AE that prolongs a pre-planned hospitalization, this event is considered an SAE and should be reported as such. Hospitalizations for elective treatments planned before screening and which are documented in the subject's source data are not regarded as SAEs.

In addition, device deficiencies, as defined in Section 12.5, that might have led to an SAE if:

- suitable action had not been taken; or
- intervention had not been made; or
- if circumstances had been less fortunate

should be categorized as an SAE and reported accordingly.

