12 SAFETY DEFINITIONS AND REPORTING REQUIREMENTS

12.1 Definition of an Adverse Event (AE)

An AE is any untoward medical occurrence, unintended disease or injury, or untoward clinical sign (including abnormal laboratory findings) in subjects, users, or other persons, whether or not related to the IMD.

Note:

- 1. This definition includes events related to the IMD.
- 2. This definition includes events related to the procedures involved.
- 3. For users or other persons, this definition is restricted to events related to the IMD.

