12.5 Definition of Device Deficiency

A device deficiency is defined as an inadequacy of a medical device with respect to its identity, quality, durability, reliability, safety, or performance.

Note: Device deficiencies include malfunctions, use errors, and inadequate labeling.

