12.6.1 Reporting and Handling of Device Deficiencies and Technical Complaints

All device deficiencies and technical complaints shall be documented and reported by the investigator throughout the clinical investigation and appropriately managed by Merz North America, Inc.

The investigator will attempt to evaluate if the deficiency or complaint might have led to an AE if suitable action had not been taken, intervention had not been made, or circumstances had been less fortunate. A device deficiency that could have led to a SADE (Section 12.4) is to be reported in the same way as an SAE.

[figure not shown]
For reporting of device deficiencies and technical complaints:

- A device deficiency/technical complaint eCRF must be completed and submitted within 24 hours by the investigational site, irrespective of the seriousness of the case.
- A device deficiency/technical complaint eCRF must be completed and submitted by the investigational site, irrespective of whether the complaint led to an AE.
- If a technical complaint or device deficiency is associated with an SAE, the investigational site must also complete and submit an SAE Report Form (Section 12.2.2) in addition to the device deficiency/technical complaint eCRF.
- If a technical complaint or device deficiency is not related to a specific subject (e.g., damaged packaging occurring prior to the subject's visit), the investigator should complete a paper device deficiency/technical complaint form, instead of the eCRF page, and send to the sponsor within 24 hours to both their clinical study representative

as well as to the Merz Technical Complaint Department for processing using the following email address: [contact].

The investigator should retain the device in question for future inspection and investigation by the sponsor, if necessary. The Merz Technical Complaint Department will decide if the device and/or supplies in question need to be returned and to whom they should be sent for investigation.

12.8 ^{CCI}

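### Protocol Section 12.2.1 classes near-miss device deficiencies as SAEs, against the SAE definition in Section 12.2 and the reporting-only rule in Section 12.6.1

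*Protocol*

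**What the plan says.** Five parts of Protocol Section 12 bear on this point.

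- **Section 12.1 (AE):** "An AE is any untoward medical occurrence, unintended disease or injury, or untoward clinical sign". The occurrence is in a person.
- **Section 12.2 (SAE):** "An SAE is an adverse event that" has one of the listed consequences. They are death, fetal harm, or an event that "led to serious deterioration in the health of the subject, that either resulted in" one of several named outcomes. All of them are things that happened.
- **Section 12.2.1 (details of an SAE):** "In addition, device deficiencies, as defined in Section 12.5, that might have led to an SAE if" action, intervention or luck had been different, "should be categorized as an SAE and reported accordingly".
- **Section 12.5 (device deficiency):** "A device deficiency is defined as an inadequacy of a medical device with respect to its identity, quality, durability, reliability, safety, or performance". No effect on a subject is needed.
- **Section 12.6.1 (handling of deficiencies):** "A device deficiency that could have led to a SADE (Section 12.4) is to be reported in the same way as an SAE". The same section requires a dedicated deficiency eCRF whether or not an AE followed. It asks for an SAE form as an extra document when an SAE is associated, and it provides for deficiencies that concern no particular subject.

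On the analysis side, Protocol Section 13.4.2 lists all AEs and SAEs and summarises TEAEs. SAP Section 6.2 likewise summarises TEAEs only. Neither visible text says how a deficiency without an adverse event is to be handled.

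**The concern.** Section 12.2.1 gives two instructions, to classify and to report. Section 12.6.1 gives only the second. The classification instruction cannot be squared with Section 12.2, because a fault that might have caused harm, but did not, is not an adverse event with a serious outcome.

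What is at stake is the meaning of the SAE data. If a site follows Section 12.2.1 literally, the SAE listing can hold entries in which no serious event took place. If another site follows Section 12.6.1, the same kind of case appears only among the deficiencies. The two sites would then record identical cases differently, and a reader of the report could not tell which SAEs were actual events. The pilot study described in Protocol Section 6.3 reported no treatment-related SAEs. If related SAEs are similarly few here, even one misclassified case would be conspicuous.

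**Working it through.** **The passages side by side**

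| Question | Section 12.2 | Section 12.2.1 | Section 12.6.1 |
|---|---|---|---|
| Must an adverse event have occurred? | Yes | No, a deficiency is enough | No, a deficiency is enough |
| Must a serious outcome have occurred? | Yes | No, a possible one is enough | No, a possible one is enough |
| Is the case classed as an SAE? | Yes | Yes | Not stated |
| Is it reported by the SAE route? | Yes (Section 12.2.2) | Yes | Yes |

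Sections 12.2.1 and 12.6.1 agree on reporting. Section 12.2.1 departs from both other sections on classification.

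**Can such a case be recorded as an AE?** Section 12.1.2 asks for a diagnosis or main symptom, an intensity and an outcome. Section 12.2.2 includes an identifiable subject in its minimum information for an initial SAE report. A near miss without an AE lacks the first three, and a deficiency tied to no subject also lacks the last. The classification rule therefore does not fit the protocol's own forms.

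**Can it reach the outputs?** Section 12.2.2 requires the eCRF to be kept consistent with SAE reports and mentions SAE reconciliation. Section 13.4.2 lists all SAEs. An item classed as an SAE under Section 12.2.1 can thus reach the listing, and no visible sentence removes it.

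**The plan's own safety figure.** Protocol Section 13.1 and SAP Section 3 give an 89.9% chance of seeing at least one event of true incidence 1.5% in 152 subjects:

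1 − (1 − 0.015)^152 = 1 − 0.1005 = 0.8995, or 89.9%.

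This reproduces. It is not an input to the point, but it shows that the plan itself takes 152 as its safety denominator.

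**Illustration of size.** Assumptions: 152 treated subjects (all those randomised), no true SAEs, and each near miss in a different subject. The intervals are exact (Clopper-Pearson) two-sided 95%.

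- With no cases, the upper limit solves (1 − p)^152 = 0.025, so p = 1 − 0.025^(1/152) = 0.0240.
- With one case, the upper limit solves (1 − p)^152 + 152·p·(1 − p)^151 = 0.025, so p = 0.0361.

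| Near misses counted as SAEs | Rate | 95% interval |
|---|---|---|
| 0 | 0/152 = 0% | 0 to 2.4% |
| 1 | 1/152 = 0.7% | 0.02 to 3.6% |
| 2 | 2/152 = 1.3% | 0.2 to 4.7% |
| 3 | 3/152 = 2.0% | 0.4 to 5.7% |

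The number treated is not given. If it were as low as the 120 planned evaluable subjects, the same formulas give 0/120 with an upper limit of 3.0%, and 1/120 = 0.8% with an upper limit of 4.6%. The picture is the same.

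**The case against.** The best defence is that Section 12.2.1 is a deliberate, cautious extension for reporting purposes. It begins by adding to the definition and says should, not must. Section 12.2.2 points investigators back to Section 12.2 for what to report as an SAE, and the separate deficiency eCRF may keep many cases out of the AE data. SAE tables and rules for deficiencies may also lie in redacted parts of the protocol or SAP. These points limit how often the problem would arise. They do not remove it, because the sentence still asks for classification as well as reporting.

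A reader might infer more than the documents support:

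- **That near misses would enter the SADE count because they concern the device.** Section 12.3 makes an ADE an AE, and Section 12.4 requires that serious consequences resulted. A near miss without an AE meets neither.
- **That they would inflate the secondary safety endpoint of related TEAEs.** TEAEs are defined as AEs with onset or worsening after first treatment (Protocol Section 13.4.2, SAP Section 6.2). A fault without an AE does not qualify.
- **That the trial's main safety conclusion would change.** SAP Section 5.2.1 has no primary safety endpoint, and no visible safety test or decision rests on an SAE count.
- **That the two sections select different cases, because one refers to an SAE and the other to a SADE.** Deficiencies include malfunctions, use errors and inadequate labelling (Section 12.5). AEs from malfunction, use error or inadequate instructions count as ADEs (Section 12.3). An SAE caused by a deficiency would ordinarily be a SADE, so the two triggers pick out nearly the same cases.
- **That every case under Section 12.2.1 is harmless.** A deficiency accompanied by a non-serious AE is also covered.

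**Conclusion.** The contradiction is in the current text. Section 12.2.1 places in the SAE class cases that Section 12.2 excludes and that Section 12.6.1 only routes for reporting. The rule itself needs correcting, since the trouble is a conflict and not a lack of detail. The consequence is limited to the SAE listing and any SAE count. The effectiveness analysis is untouched.

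The size is minor. One case would add 0.7 percentage points to the apparent SAE rate and raise its upper limit from 2.4% to 3.6%. That rests on assuming 152 treated subjects and no true SAEs of any cause. The second assumption is only for illustration, since the pilot result concerns treatment-related SAEs. Whether any near miss will occur cannot be judged from the documents, and redacted text may already deal with such cases.

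**What to change.** In Protocol Section 12.2.1, replace "should be categorized as an SAE and reported accordingly" with the Section 12.6.1 form, namely that such a deficiency "is to be reported in the same way as an SAE". Use one trigger wording in both sections.

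Add a sentence to SAP Section 6.2, for example: Device deficiencies are tabulated separately, and a deficiency contributes to SAE listings and counts only if an adverse event meeting Protocol Section 12.2 occurred.

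Neither change alters who reports, by what route or how fast, so vigilance is unaffected. The cost is a minor protocol wording amendment, which needs written IEC/IRB approval under Protocol Section 14.6, and one SAP sentence. Protocol Section 13 already allows for an SAP update before the final database close.

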12.2.2 Reporting and Handling of an SAE

All SAEs that occur during the clinical study period, whether considered to be related to an IMD or not, must be reported via fax, telephone, or e-mail, and an SAE Report Form should be submitted to the sponsor immediately upon knowledge of the event. Further reporting details will be outlined in a separate document.

Although all information required for completion of an SAE Report Form may not be available within the specified time period, an initial report should be submitted if the following minimal information is available:

- An identifiable subject (unique subject number);
- A suspect product and how the treatment relates to the SAE;
- An identifiable reporting source (investigator/study site identification); and/or
- An event or outcome that can be identified as serious.

The investigator must report SAEs to Merz as defined in Section 12.2 and the site's IEC/IRB per their reporting guidelines. Within 10 working days after Merz first receives notice of the SAE, Merz Product Safety will conduct an evaluation of the SAE and report the results of such evaluation to regulatory agencies, IECs/IRBs, and investigators, as applicable.

The investigator must supply further supporting information, and a detailed SAE description is an integral part of this supporting information. Follow-up SAE reports should be sent without delay to the sponsor as an SAE Report Form (marked as a "follow-up" report), and the eCRF has to be updated accordingly to avoid discrepancies. The SAE has to be followed until the SAE is resolved/recovered or a plausible explanation is available. The SAE will be followed-up only in the Global Product Safety database after final SAE reconciliation is completed.

An SAE occurring after the end of the observational period would need to be reported if the investigator considers the event to be related to IMD. These reports generally will not be entered into the investigation database. Following database close (including main and safety follow-up periods), any ongoing SAEs will be followed until resolution or stabilization under the responsibility of the investigator per his/her standard of care.

The investigator should complete and send any SAE Report Forms (including any follow-up forms) to Merz North America Product Safety via the email provided below:

Merz North America, Inc. Product Safety [name]

Product Safety Email: [contact]

12.3 Definition of an Adverse Device Effect (ADE)

An ADE is defined as an AE related to the use of an IMD.

Note:

- 1. This definition includes AEs resulting from insufficient or inadequate instructions for use, deployment, implantation, installation, or operation or any malfunction of the IMD.
- 2. This definition includes any event resulting from use error or from intentional misuse of the IMD.

12.4 Definition of a Serious Adverse Device Effect (SADE)

A SADE is defined as an adverse device effect that has resulted in any of the consequences characteristic of an SAE (Section 12.2).

12.4.1 Definition of an Anticipated Serious Adverse Device Effect (ASADE)

An ASADE is a serious adverse device effect which by its nature, incidence, severity, or outcome has been identified in the current version of the risk-analysis report.

12.4.2 Definition of an Unanticipated Adverse Device Effect (UADE)

A UADE is defined as follows:

Any serious adverse effect on health or safety or any life-threatening problem or death caused by, or associated with, a device, if that effect, problem, or death was not previously identified in nature, severity, or degree of incidence in the investigational

plan or application (including a supplementary plan or application), risk analysis report, or IFU.

• Any other unanticipated serious problem associated with a device that relates to the rights, safety, or welfare of subjects.

12.5 Definition of Device Deficiency

A device deficiency is defined as an inadequacy of a medical device with respect to its identity, quality, durability, reliability, safety, or performance.

Note: Device deficiencies include malfunctions, use errors, and inadequate labeling.

12.6 Definition of Technical Complaint

A technical complaint, also referred to as a product complaint, is an apparent or suspected deficiency of a product in which the product does not meet its specification (e.g., leaking tube, incorrect consistency, cracked vial).

12.6.1 Reporting and Handling of Device Deficiencies and Technical Complaints

All device deficiencies and technical complaints shall be documented and reported by the investigator throughout the clinical investigation and appropriately managed by Merz North America, Inc.

The investigator will attempt to evaluate if the deficiency or complaint might have led to an AE if suitable action had not been taken, intervention had not been made, or circumstances had been less fortunate. A device deficiency that could have led to a SADE (Section 12.4) is to be reported in the same way as an SAE.

[figure not shown]
For reporting of device deficiencies and technical complaints:

- A device deficiency/technical complaint eCRF must be completed and submitted within 24 hours by the investigational site, irrespective of the seriousness of the case.
- A device deficiency/technical complaint eCRF must be completed and submitted by the investigational site, irrespective of whether the complaint led to an AE.
- If a technical complaint or device deficiency is associated with an SAE, the investigational site must also complete and submit an SAE Report Form (Section 12.2.2) in addition to the device deficiency/technical complaint eCRF.
- If a technical complaint or device deficiency is not related to a specific subject (e.g., damaged packaging occurring prior to the subject's visit), the investigator should complete a paper device deficiency/technical complaint form, instead of the eCRF page, and send to the sponsor within 24 hours to both their clinical study representative

as well as to the Merz Technical Complaint Department for processing using the following email address: [contact].

The investigator should retain the device in question for future inspection and investigation by the sponsor, if necessary. The Merz Technical Complaint Department will decide if the device and/or supplies in question need to be returned and to whom they should be sent for investigation.

12.8 ^{CCI}

12.9 Reporting of Pregnancy

Any pregnancy that starts during the clinical study must be reported, using the Pregnancy Form, by the investigator to the sponsor within 24 hours of learning of its occurrence. Pregnancies and pregnancy follow-up should be reported on a Pregnancy Form. Pregnancy follow-up should describe the outcome of the pregnancy, including any voluntary or spontaneous discontinuation; details of the birth; the presence or absence of any congenital abnormalities, birth defects, maternal or newborn complications, and their relation to the IMD. In addition, each pregnancy has to be reported on the AE eCRF (i.e., as a non-serious AE due to device exposure before or during pregnancy). Pregnancy Forms (including any follow-up forms) should be submitted to the contacts referenced in Section 12.2.2.

If a subject becomes pregnant during the study, the subject must not receive further treatments (i.e., additional treatments or optional retreatment); however, the subject will remain in the study.

13 STATISTICAL METHODS

This section describes the statistical analyses foreseen at the time of study planning.

CCI

Further details on the statistical and analytical aspects will be presented in the statistical analysis plan (SAP) that will be prepared and completed prior to database close of the main period. If needed, the SAP will be updated before database close after the safety extension period (including data of main and safety follow-up periods).

[figure not shown]
Any deviations from planned analyses, the reasons for such deviations, and all alternative or additional statistical analyses that may be performed before database close, will be described in amendments to the CSP and/or the SAP. All deviations and/or alterations will also be summarized in the clinical study report.

In the event of a pandemic disease outbreak (e.g., new COVID-19 public health emergency), if on-site visits are not possible due to site closures, travel limitations, or other considerations (e.g., if site personnel or trial subjects become infected with SARS-CoV-2), the following mitigations should be considered and assessed in an updated SAP:

- Changes to planned and additional analyses due to the public health emergency should be described. Drop-out patterns and sources of bias such as missing values and virtual instead of live assessments (if applicable) should be thoroughly assessed.
- Systematic identification of protocol deviations due to the pandemic should be included.
- The need for involvement of an independent Data Monitoring Committee should be considered, particularly if trial sample size changes are anticipated.

13.1 Estimation of Sample Size

The primary effectiveness analysis considers the proportion of subjects with at least 1-point (≥ 1-point) improvement on the MAS Décolleté Wrinkles-At Rest scale at Week 24 compared to baseline as assessed live by a blinded evaluator. Subjects will be randomized into two treatment groups as detailed in Section 13.2.

approximately 152 subjects, 114 subjects in the treatment Group A and 38 subjects in the untreated-control/delayed-treatment Group B, will be randomized for this study. Regarding the safety evaluation, in a sample size of 152 subjects an adverse event with a true incidence of 1.5% will be observed at least once with a probability of 89.9%.

Sample size calculations were performed using nQuery software (Version 8.5, Statistical Solutions Ltd., 2019).

13.2 Randomization

All eligible subjects will be randomized 3:1 to one of the following groups:

- Group A: Treatment with diluted Radiesse at Day 1, Week 6, and Week 12.
- Group B: Untreated control followed by delayed treatment with diluted Radiesse at Week 24 (after primary endpoint assessment), Week 30, and Week 36.

The randomization will be block-stratified by study site as described in Section 10.3.

